#### 5.5.2.1 Procedures for Discontinuation of Protocol-Specified Treatment Requirements

Whenever possible, subjects who received an abbreviated infusion that was terminated due to a possible infusion reaction should complete all remaining scheduled study visits including all exams, procedures, assessments, and tests. Furthermore, if discontinuation is due to safety concerns, subjects will be given appropriate care under medical supervision beyond the last scheduled study visit, if necessary, until the symptoms of any AE resolve or the subject's condition becomes stable. If the site PI determines that completion of these visits is not clinically appropriate for the subject or if the subject elects not to complete these visits, the subject will be withdrawn from the study per the guidelines in Section 5.5.3.1, *Procedures for Subject Withdrawal from the Study*.

### 5.5.3 Subject Withdrawal from the Study

When a subject is withdrawn from the study, protocol-specified treatment requirements are discontinued, and study-related visits, exams, procedures, assessments, tests, and data collection are terminated. Individual subjects will be withdrawn from the study under the following conditions:

1. The subject did not receive the planned infusion after two blood donations for PolyTreg manufacturing
2. The subject withdraws consent
3. The investigator or NIAID believes it is in the best interest of the subject
4. The subject is lost to follow-up

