## 3.2 Description of Primary Endpoint

### 3.2.1 Primary Safety Endpoint

The primary study endpoint is the number of significant events in each cohort through Week 52, defined as any related NCI-CTCAE Grade 3 or higher AE or any related SAE.

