#### 5.5 Treatment Interruption and Discontinuation

Treatment will consist of a single infusion of *ex vivo* expanded PolyTregs. Once a PolyTreg infusion has concluded, the treatment phase of the protocol is complete. Thus, the question of subsequent withdrawal from treatment will not arise. Therefore, all subjects who undergo an infusion will continue per protocol unless they choose to withdraw (see Section 5.5.3, *Subject Withdrawal from the Study*).

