### 5.5.2 Criteria for Permanent Discontinuation of Study Treatment

Study treatment will be discontinued permanently for any individual subject under the following conditions:

1. At any time prior to or during the PolyTreg infusion at the request of the subject
2. If investigators or NIAID determine that the subject's health, safety, and/or well-being are threatened
3. If an infusion reaction symptom that caused a slow or temporary stop of the infusion cannot be resolved with acetaminophen or diphenhydramine
4. If administration of glucocorticoids to treat an infusion reaction is required
5. If a subject experiences any of the following:
  - a. NCI-CTCAE Grade 3 or higher infusion-related reaction
  - b. NCI-CTCAE Grade 3 or higher cytokine release syndrome
  - c. Any other infusion related SAE

Subjects who discontinue protocol-specified treatment will be treated as medically indicated according to physician discretion. Refer to Section 5.5.3.1, *Procedures for Subject Withdrawal from the Study*.

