#### 5.5.3.1 Procedures for Subject Withdrawal from the Study

Whenever possible, subjects who withdraw from the study will be asked to consent to an end-of-study evaluation, in which all scheduled exams, procedures, and laboratory tests

planned for Week 12 will be performed; unless the early withdrawal is after that time, in which case all scheduled exams, procedures, and laboratory tests scheduled for Week 52 will be performed; unless the early withdrawal is after that time, in which case all scheduled exams, procedures, and laboratory tests scheduled for Week 156 will be performed. Furthermore, if discontinuation is due to safety concerns, subjects will be given appropriate care under medical supervision beyond the last scheduled study visit, if necessary, until the symptoms of any AE resolve or the subject's condition becomes stable. After this end-of-study visit, the PI (or designated treating physician) may continue to follow the subject to manage clinical care, but no additional study-related data will be collected.

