#### 8.3.1 Safety Analysis

All safety summaries will be performed using the Safety population.

AEs including changes in laboratory values will be graded according to the NCI-CTCAE Version 4.0 (<http://ctep.cancer.gov/reporting/ctc.html>). The frequency of AEs will be summarized by system organ class, preferred term, severity (grade), and relationship to PolyTregs as specified by the SRC and by the site. Relationship to PolyTregs will be categorized as either related (possibly, probably, or related) or unrelated (unlikely or not related). For the primary safety endpoint defined in Section 3.2.1, *Primary Safety Endpoint*, and each key safety endpoint defined in Section 3.3.1, *Secondary Safety Endpoints*, the number and percentage of subjects experiencing the event will be summarized.

Pemphigus flares defined in Section 3.4.1, *Exploratory Safety Endpoints*, will be summarized separately through Week 156 using appropriate descriptive statistics.

Laboratory results by parameter will be displayed in listings and graphically, where appropriate, to illustrate changes in laboratory results over time.

SAEs will also be summarized using the donation population to assess SAEs occurring from donation until PolyTreg infusion.

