#### **11.5 Study Termination**

In the event that the study is terminated, subjects who have received study treatment will be followed for the study's three years of safety follow-up.

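### Sections 5.5 to 5.5.3.1 disagree on follow-up of an infused subject taken off treatment or study, and after withdrawal later first-year safety events go uncollected

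*Combined protocol and SAP*

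**What the plan says.** Four neighbouring sections govern what happens once cells have been infused.

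- Section 5.5: "all subjects who undergo an infusion will continue per protocol unless they choose to withdraw".
- Section 5.5.2 lists the reasons for permanent discontinuation, then says: "Subjects who discontinue protocol-specified treatment will be treated as medically indicated according to physician discretion". It next refers the reader to Section 5.5.3.1, the procedure for leaving the study.
- Section 5.5.2.1: whenever possible, "subjects who received an abbreviated infusion that was terminated due to a possible infusion reaction should complete all remaining scheduled study visits". The site PI may decide that this is not clinically appropriate, or the subject may decline; the subject is then withdrawn.
- Section 5.5.3 allows withdrawal when the investigator or NIAID thinks it best for the subject (item 3). On withdrawal, "study-related visits, exams, procedures, assessments, tests, and data collection are terminated".

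Section 5.5.3.1 asks the leaver to consent to one end-of-study evaluation, using the Week 12, 52 or 156 assessments according to timing. After that visit the physician "may continue to follow the subject to manage clinical care, but no additional study-related data will be collected".

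On analysis, Section 3.2.1 makes the primary endpoint the "number of significant events in each cohort through Week 52". Section 8.2.2 puts every infused subject in the safety population, Section 8.3.1 says "the number and percentage of subjects experiencing the event will be summarized", and Section 8.5.4 rules out imputation.

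**The concern.** The exposure is one infusion that cannot be taken back, and the primary question is what related harm follows within 52 weeks. Stopping an infusion, or ending a subject's visits, does not end that exposure. Yet the sections do not agree on whether such a subject stays in follow-up, and the withdrawal route ends data collection without asking whether the subject would still accept a telephone call or a records check.

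Two things are at stake. The first is the endpoint: an event at Week 30 in a subject withdrawn at Week 6 is not recorded. The second is monitoring. Section 3.1 suspends enrollment after a Grade 3 or higher AE or any SAE in a subject's first year, and Section 5.5.4 lists first-year events that need DSMB input, including repeated Grade 3 events under one preferred term in a cohort. An event that nobody collects can trigger neither. In a cohort of 4 to 6, a single subject matters.

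**Working it through.** **1. The passages side by side**

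- Who can end participation after infusion? Section 5.5: only the subject. Section 5.5.3 item 3: also the investigator or NIAID. Section 5.5.2.1: also the site PI. These cannot all hold.
- What happens when an infusion is cut short for a possible reaction? Section 5.5.2 points to the withdrawal procedure; Section 5.5.2.1 keeps the subject on all visits. The same subject falls under both.
- What happens when it is cut short for another reason (Section 5.5.2 items 1 and 2)? Section 5.5.2.1 is silent. The reader has the pointer in 5.5.2 and the general sentence in 5.5, which lead in different directions.
- What is collected after withdrawal? At most the end-of-study evaluation, then nothing.

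**2. The plan's own figures**

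Table 8.1 gives the chance of at least one event among n subjects, P = 1 − (1 − p)^n, at p = 0.1, 0.2 and 0.3:

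- n = 4: 0.3439, 0.5904, 0.7599 (stated 0.34, 0.59, 0.76)
- n = 6: 0.4686, 0.7379, 0.8824 (stated 0.47, 0.74, 0.88)

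All six cells reproduce. The formula treats every subject as fully observed for the event.

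**3. Effect of early leavers on detection**

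The documents give no dropout rate, so these are scenarios. Let w of n infused subjects leave, with a fraction f of their Week 52 event risk observed beforehand, and no replacement:

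P = 1 − (1 − p)^(n−w) × (1 − f·p)^w

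| n | w | f | p = 0.1 | p = 0.2 | p = 0.3 |
|---|---|---|---|---|---|
| 4 | 0 | – | 0.34 | 0.59 | 0.76 |
| 4 | 1 | 0 | 0.27 | 0.49 | 0.66 |
| 4 | 1 | 0.5 | 0.31 | 0.54 | 0.71 |
| 4 | 2 | 0 | 0.19 | 0.36 | 0.51 |
| 6 | 1 | 0 | 0.41 | 0.67 | 0.83 |

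For example, 1 − 0.8³ = 0.488.

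**4. Follow-up lost**

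One of 4 subjects leaves at Week 6, losing 52 − 6 = 46 weeks.

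- Not replaced: 46 / (4 × 52) = 46/208 = 22%.
- Replaced: 46 / (5 × 52) = 46/260 = 18%.

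Which case applies is itself unclear. Section 3.1.2.1 replaces only non-safety withdrawals before Week 12; Section 8.5.4 replaces any infused subject who does not complete 12 weeks. If the leaver is replaced, four subjects are again fully followed and detection at p = 0.2 returns to at least 0.59, but the leaver stays in the denominator. Neither section replaces anyone who leaves between Weeks 12 and 52.

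**5. Effect on the reported percentage**

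The expected safety-population percentage is p × (n − w + w·f) / n. At p = 0.2, n = 4, w = 1, f = 0 and no replacement, this is 0.2 × 3/4 = 15% against a true 20%. With replacement it is 0.2 × 4/5 = 16%.

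In a single cohort of 4 where one subject has an event and a different one leaves early, the result is 1/4 = 25% of the safety population, 1/3 = 33.3% of those fully followed, and 2/4 = 50% if the leaver is counted as having an event.

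**The case against.** Several stronger readings are tempting, and the documents do not support them.

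- *Section 11.5 contradicts Section 5.5.3.* It does not. It says that "subjects who have received study treatment will be followed for the" planned three years when the whole study is terminated; 5.5.3 concerns one subject. Both can be followed. The contrast shows only that the sponsor accepts long follow-up of infused subjects when the trial closes.
- *All data collection stops at withdrawal.* Section 5.5.3.1 adds an end-of-study evaluation if the subject consents.
- *The plan counts leavers as event-free.* No section says so, and declining to impute is not the same as imputing zero. It is what an all-infused denominator and a simple percentage produce by default. Section 8.5.5 leaves details to a later SAP, and listings in a trial of at most 12 infused subjects would make each leaver visible.
- *Every safety exit biases the result downward.* A subject stopped for a Grade 3 or higher infusion reaction, Grade 3 or higher cytokine release syndrome, or an infusion-related SAE will normally already have a significant event if it is judged related. Later events do not change the percentage of subjects affected. The loss arises for subjects without a prior significant event; Section 5.5.2 items 1 to 4 do not require one.
- *Anyone stopped under items 1 or 2 is withdrawn.* This argues from silence. Those items can also apply before any infusion, where the pointer to 5.5.3.1 makes sense.

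It is also fair to say that early exits may be rare: all 14 treated subjects in the T1DM trial completed follow-up (Section 1.3.2.1.1). Evidence that infused cells persist should be used with care. Detection to 365 days was in the cohort given about 2.6 × 10^9 cells, roughly ten times this trial's top target of 2.5 × 10^8. The slow-phase half-life of a year or more in 4 of 7 patients pools two dose groups.

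These points narrow the claim but leave its core standing. A later SAP can settle the reporting; it cannot recover data that the protocol tells sites not to collect.

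**Conclusion.** The concern holds in a limited form. Sections 5.5, 5.5.2, 5.5.2.1 and 5.5.3 are inconsistent on who stays in follow-up, and a withdrawn infused subject contributes no study data after at most one further visit. Events between that visit and Week 52 are lost to the primary endpoint and to the first-year safety triggers. The plan does not say how incomplete Week 52 follow-up is reported.

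The size depends on dropout, which the documents do not give. For one early leaver among 4 without replacement, detection at p = 0.2 lies between 0.49 (no risk observed before leaving) and 0.54 (half observed), against the tabulated 0.59. These figures assume independent subjects and that leaving is unrelated to risk. If those removed are at higher risk than the rest, the loss is greater.

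A reader might infer a planned bias, or a conflict with Section 11.5; neither is in the text. This should be corrected, but it does not undermine the design.

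**What to change.** 1. In Sections 5.5.3 and 5.5.3.1, for any subject who received any part of the infusion and has not withdrawn consent to data collection, keep collecting Grade 3 or higher AEs and SAEs with attribution, by telephone or from records, through Week 52 and then Week 156.
2. Reconcile Sections 5.5, 5.5.2, 5.5.2.1 and 5.5.3 so that stopping the infusion is distinct from leaving the study, and keep a stated procedure for subjects who stop before any infusion. Who may stop treatment or withdraw a subject is for the sponsor to decide; the point here is that the sections must agree.
3. Reconcile Sections 3.1.2.1 and 8.5.4 on whether an infused subject who leaves for safety reasons before Week 12 is replaced.
4. In Section 8.3.1, and in the later SAP, show beside each Week 52 and Week 156 percentage the number of subjects followed to that week or to an event.

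The cost is protocol wording, one extra column in the safety tables, and a few calls by existing site staff for the occasional early leaver. The downside is that events collected remotely carry less detail, which may make grading and attribution less certain.

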#### 5.5.3.1 Procedures for Subject Withdrawal from the Study

Whenever possible, subjects who withdraw from the study will be asked to consent to an end-of-study evaluation, in which all scheduled exams, procedures, and laboratory tests

planned for Week 12 will be performed; unless the early withdrawal is after that time, in which case all scheduled exams, procedures, and laboratory tests scheduled for Week 52 will be performed; unless the early withdrawal is after that time, in which case all scheduled exams, procedures, and laboratory tests scheduled for Week 156 will be performed. Furthermore, if discontinuation is due to safety concerns, subjects will be given appropriate care under medical supervision beyond the last scheduled study visit, if necessary, until the symptoms of any AE resolve or the subject's condition becomes stable. After this end-of-study visit, the PI (or designated treating physician) may continue to follow the subject to manage clinical care, but no additional study-related data will be collected.

#### 5.5.4 Safety Stopping Guidance

The SRC will suspend enrollment after a Grade 3 or higher AE or any SAE (as described in Section 3.1, *Description of Study Design*) in this trial in order to review the event, to review any additional events that occurred in the trial, and to make a decision on how to proceed. In the event of a temporary suspension in enrollment for a Grade 3 or higher AE or any SAE or a post release positive sterility result (see Section 5.3.3, *Action Plan for Post Release Positive Sterility Results*), no new subjects will be consented or started on therapy with PolyTregs; subjects who already received PolyTregs will continue to be followed. Subjects in the screening phase of the study may continue screening procedures (e.g., blood tests), but a skin biopsy to confirm Inclusion Criteria # 3 (see Section 4.1, *Inclusion Criteria*) should be deferred. Enrollment will not occur until the SRC review is complete.

A significant event in this trial can occur either due to toxicity from the study drug or disease worsening (e.g., a pemphigus relapse/flare) assessed as related to the investigational treatment.

The SRC will make this determination, seeking advice from the DSMB, if necessary. After SRC review, the study will: 1) proceed with enrollment as originally planned, 2) continue to suspend enrollment until the DSMB can review and advise on the event, or 3) be placed on hold pending further evaluation of the event, consideration of potential study modifications, and review by the DSMB, IRB and FDA.

For Grade 3 or higher AEs or any SAEs occurring in the first year of the study for each participant, DSMB input will be required for the evaluation of the following events unless the event was judged clearly unrelated to the investigational treatment:

- two Grade 3 or higher AEs or SAEs that occurs during the first 12 weeks of each participant in each cohort
- any Grade 4 or 5 AE
- two or more Grade 3 AEs of the same preferred term in a cohort
- any Grade 3 AE that is part of a pemphigus relapse/flare using the consensus definition of 3 or more new lesions a month that do not heal spontaneously within 1 week or by the extension of established lesions in a patient who has achieved disease control [58]

For Grade 3 or higher AEs or any SAEs occurring in the second or third years of the study for each participant, DSMB input will be required for the evaluation of the following events unless the event was judged clearly unrelated to the investigational treatment:

- any Grade 4 or 5 AE
- two or more Grade 3 AEs of the same preferred term in a cohort

In addition to the pre-scheduled data reviews and planned safety monitoring, the DSMB will review any event that potentially impacts safety at the request of the SRC or DAIT, NIAID. The DSMB will have the discretion to recommend actions regarding study conduct and continuation as a consequence of any planned or unplanned monitoring activity.

Otherwise, the DSMB will be informed in real time per the following criteria:

- During Year 1 of each subject's participation:
  - any decision of the SRC to add additional subjects based on confirmation of a significant event (as defined as any related Grade 3 or higher AEs or any SAEs)
  - any malignancy
- During Years 2 and 3 of each subject's participation:
  - any Grade 3 event that is part of a pemphigus relapse/flare using the consensus definition of 3 or more new lesions a month that do not heal spontaneously within 1 week or by the extension of established lesions in a patient who has achieved disease control [58]
  - any malignancy

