## 3 STUDY DESIGN

### 3.1 Description of Study Design

This phase I trial will be conducted as an open-label, dose-escalation, multicenter trial in adult patients with active pemphigus. We expect approximately four clinical sites to participate (UCSF and approximately 3 remote sites). The study will employ a sequential dose-escalation design with a maximum of twelve subjects receiving a single infusion of *ex vivo* selected and expanded autologous PolyTregs. The primary study endpoint is the number of significant events, defined as any related NCI-CTCAE Grade 3 or higher AE or any related SAE. Related is defined as being possibly related or related to the *ex vivo* expanded autologous PolyTregs, as determined by the safety review committee (SRC, consisting of the protocol chair, representatives from the DAIT-Statistical and Clinical Coordinating Center [DAIT-SACCC], and representatives of DAIT) that will review the laboratory data and clinical experience of all subjects in the cohort. Pemphigus relapses/flare will be assessed using the consensus definition of 3 or more new lesions a month that do not heal spontaneously within 1 week or by the extension of established lesions in a patient who has achieved disease control [58]; however, only flare components assessed as AEs of NCI-CTCAE Grade 3 or higher or SAEs will contribute to the evaluation of significant events.

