**Table 3.1 Dose cohorts for the Study**

Cohort	Subjects #	Target Cell Dose	Allowable Dose Range (-30% to +20%)	Volume (ml)	Concentration (cells/ml)	Allowable Concentration Range (-30% to +20%)
1	4-6	$1.0 \times 10^8$	$0.7 \times 10^8$ to $1.2 \times 10^8$	100	$1.0 \times 10^6$	$0.7 \times 10^6$ to $1.2 \times 10^6$
2	4-6	$2.5 \times 10^8$	$1.75 \times 10^8$ to $3.0 \times 10^8$	100	$2.5 \times 10^6$	$1.75 \times 10^6$ to $3.0 \times 10^6$

Two dosing groups will be employed in this trial:  $1.0 \times 10^8$  and  $2.5 \times 10^8$  PolyTregs. Each cohort will enroll 4-6 subjects with pemphigus. Each subject in cohorts 1 and 2 will receive an infusion and must reach Week 2 prior to the subsequent subject's blood donation. A schematic representation of an individual's participation is shown in Figure 1. The study dose can be escalated after the DSMB and SRC evaluates the safety data collected when the fourth subject in cohort 1 completes Week 8. After reviewing the data from the first four subjects, the DSMB and SRC will recommend adding additional subject(s) to the first cohort, advancing enrollment in the second cohort, or stopping the trial. A schematic representation of the study's cohort design is shown in Figure 2.

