Since a significant event in this trial can occur from toxicity from the study drug or disease worsening (e.g., a pemphigus flare), the standard 3 + 3 design rules for dose escalation will not be employed. Therefore, if a Grade 3 or higher AE or any SAE occurs in a subject during his/her first year of study participation, enrollment will be suspended until the SRC can convene to review the event. If this occurs, the SRC may decide at that time to proceed with enrollment, adjust the dose as described above, continue the suspended enrollment until the Data and Safety Monitoring Board (DSMB) can review the data, or place the trial on hold. The SRC will review all Grade 3 or higher AEs or any SAEs that occur throughout the study. However, since the likelihood of events being related to the investigational treatment diminishes over time, Grade 3 or higher AEs or any SAEs occurring during a subject's second or third year of the study will not result in an immediate suspension of enrollment, donation, and treatment, unless the SRC determines that such action is indicated. Provided the SRC can review the event within 5 business days of awareness, events judged to be significant will drive protocol management in terms of proceeding, suspending enrollment/treatment pending ad hoc DSMB input, or placing the study on hold pending further evaluation.

DSMB input will be required for the evaluation of some specific events. Description of these events and additional directives are outlined in Section 5.5.4, *Safety Stopping Guidance*.

Accrual of all subjects is expected to take approximately 1.5 years.

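### No mandatory DSMB trigger counts repeat Grade 3 events across the two dose cohorts, so a same-term pair with one event at each dose does not by itself require DSMB input

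*Combined protocol and SAP*

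**What the plan says.** Section 5.5.4 has two lists of events that require DSMB input. The first covers Grade 3 or higher AEs and SAEs "occurring in the first year of the study for each participant, DSMB input will be required for the evaluation of the following events"; the second covers those "occurring in the second or third years of the study for each participant, DSMB input will be required". Both exempt an event by the same clause: "unless the event was judged clearly unrelated to the investigational treatment". The repeat-event item, "two or more Grade 3 AEs of the same preferred term in a cohort", stands in both lists with the same wording.

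The other mandatory triggers are:
- any Grade 4 or 5 AE, in either list;
- in the first-year list only, a single Grade 3 AE that is part of a pemphigus flare;
- in the first-year list only, two Grade 3 or higher AEs or SAEs in participants' first 12 weeks, stated by cohort.

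Section 3.1 adds that "if a Grade 3 or higher AE or any SAE occurs in a subject during his/her first year of study participation", enrollment is suspended until the SRC has met. The SRC reviews all Grade 3 or higher AEs and SAEs throughout the study. Under Section 5.5.4 the SRC or the sponsor may ask the DSMB to look at any event. Section 7.8.3 schedules DSMB review when the fourth cohort 1 subject completes Week 8 and then at least yearly, with listings of all reported AEs and SAEs.

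On size, "Each cohort will enroll 4-6 subjects with pemphigus", with a "maximum of twelve subjects receiving a single infusion".

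**The concern.** The repeat-event item is the rule that brings a recurring, non-life-threatening toxicity to the independent board. The two cohorts receive the same kind of product at target doses of 1.0 × 10^8 and 2.5 × 10^8 cells, a 2.5-fold difference. A toxicity of the product, rather than of one dose, could well show itself once in each cohort. Under the wording, such a pair triggers nothing mandatory. Because the 12-week item is also stated by cohort, this holds even if both events are possibly related and both fall within 12 weeks of infusion.

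What remains is a decision by the SRC, which Section 3.1 composes of the protocol chair, coordinating-center representatives and sponsor representatives, or else the next scheduled DSMB meeting. No scheduled DSMB review is tied to a milestone in cohort 2. In a trial of at most 12 subjects that does not use 3 + 3 rules, these triggers carry much of the formal protection.

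The text is also silent on a pair with one event in a participant's first year and the other in a second or third year.

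**Working it through.** **The plan's own figure.** Table 8.1 gives the probability of at least one event, 1 − (1 − p)^n. For p = 0.1, 0.2 and 0.3 this is 0.344, 0.590 and 0.760 with n = 4, and 0.469, 0.738 and 0.882 with n = 6. All six cells reproduce. The documents give no operating figure for the DSMB trigger.

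**Inputs.** Cohort sizes of 4 to 6 come from Table 3.1, and follow-up of 156 weeks from Section 3.1.2.1. How events divide between cohorts and over time is not given, so it is assumed and varied below.

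**Step 1: cohort limit alone.** Take two same-term Grade 3 events in different subjects, neither exempt, with equal risk per subject.

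P(same cohort) = [C(n1,2) + C(n2,2)] / C(n1+n2,2)

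- 6+6: (15 + 15)/66 = 0.4545; missed 54.5%
- 4+4: (6 + 6)/28 = 0.4286; missed 57.1%
- 4+6: (6 + 15)/45 = 0.4667; missed 53.3%

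These shares apply if all events fall in the first year, or if straddling pairs count.

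**Step 2: risk rising with dose.** If each cohort 2 subject has r times the risk of a cohort 1 subject:

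P(same cohort) = [C(n1,2) + r²C(n2,2)] / [C(n1,2) + r²C(n2,2) + r·n1·n2]

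With r = 3:
- 4+6: 141/213 = 0.662; missed 33.8%
- 6+6: 150/258 = 0.581; missed 41.9%
- 4+4: 60/108 = 0.556; missed 44.4%
- 6 in cohort 1 and 4 in cohort 2: 69/141 = 0.489; missed 51.1%

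**Step 3: adding a strict year limit.** If both events must also fall in the same list's period, and q is the share of events in the first year, multiply by P(same period) = q² + (1 − q)². Equal risk:

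| q | q² + (1 − q)² | missed, 6+6 |
|---|---|---|
| 1/3 (uniform over three years) | 0.556 | 74.7% |
| 0.5 | 0.500 | 77.3% |
| 0.7 | 0.580 | 73.6% |
| 0.9 | 0.820 | 62.7% |
| 1.0 | 1.000 | 54.5% |

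With 4+4 and q = 1/3 the share is 76.2%. Over all cohort sizes, r from 1 to 3 and q from 1/3 to 1, the missed share runs from 34% to 79%.

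**Step 4: more than two events.** If only the cohort limit applies, three non-exempt events in two cohorts must put at least two in one cohort, so the trigger is met. With the strict year limit, uniform timing and 6+6, three events in different subjects meet it with probability 63.6%, and four with 91.0%.

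**Step 5: effect of the change.** In the 6+6 uniform case, 25.3% of pairs meet the trigger under the strictest reading. Removing only the year limit gives 45.5%, removing only the cohort limit 55.6%, and removing both 100%.

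**The case against.** Counting per dose cohort is an ordinary choice in dose escalation, and the other safeguards are real.

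- Until escalation, every pair lies within cohort 1.
- Each first-year Grade 3 or higher AE suspends enrollment while the SRC reviews it together with other events in the trial, which is a look across cohorts.
- A single first-year Grade 3 flare event or any Grade 4 or 5 AE already goes to the DSMB unless clearly unrelated. In years two and three, Grade 3 flare events are notified to it in real time.
- Expedited safety reports also reach the DSMB promptly (Section 7.8.3).
- A trial-wide count could send the board two events that are years apart, although Section 3.1 says relatedness becomes less likely with time.

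All of this stands, and it limits the consequence. It does not fill the gap, because SRC referral is discretionary and the scheduled DSMB review may be up to a year away. The exemption for clearly unrelated events already restrains the late pairs. The 12-week item is awkwardly worded; even if it were read as trial-wide, it would help only when both events fall in the first 12 weeks.

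A reader might infer several stronger claims that the documents do not support:

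- *That about three quarters of repeat pairs never require DSMB input.* This needs many events after the first year, against the premise in Section 3.1, and a year limit on the pair that the text does not state. It also ignores the other triggers.
- *That staggered enrollment splits pairs between the two lists.* The periods are in each participant's own time. Two subjects infused 18 months apart, each with an event at their own Week 10, fall in the same period.
- *That the first year starts at consent, leaving the end of the primary window under the second-year rules.* No section says so. The primary endpoint ("The primary study endpoint is the number of significant events in each cohort through Week 52") and the Week 156 completion visit follow a schedule centered on infusion, and AE recording changes at Week 52 (Section 7.3.3.1). Years counted from consent would leave the last weeks before Week 156 in a fourth year with no rule.

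**Conclusion.** The point holds as a specific gap. Two non-exempt Grade 3 AEs of the same preferred term, one in each cohort and neither part of a first-year flare, do not require DSMB input. That follows from the wording and needs no assumption.

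How often it would matter does need assumptions. For two events in different subjects at equal risk, the cohort limit misses 54.5% (6+6) or 57.1% (4+4). With threefold risk in cohort 2 it misses 33.8% (4+6) or 41.9% (6+6), and up to 51.1% if cohort 1 is the larger. About 75% is the result of one particular set of assumptions and should not be quoted as the size of the gap. The gap concerns the first repeat: SRC review and at least yearly DSMB review continue, and a third same-term event would usually meet the trigger. Whether straddling pairs count, and when the first year begins, are matters for clarification and not demonstrated errors.

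**What to change.** In both lists of Section 5.5.4, replace the cohort restriction in "two or more Grade 3 AEs of the same preferred term in a cohort" with a count *in the trial, in either cohort*, and keep the exemption for events judged clearly unrelated.

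Add one sentence saying that events in the first year and in years two and three count together, so that an earlier first-year event counts toward a pair completed later.

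As a clarification only, state in Sections 3.1 and 5.5.4 that the first year means through Week 52 after infusion.

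The cost is a few sentences and, in at most 12 subjects, a few more ad hoc DSMB reviews, some of them for events far apart in time. Cohort sizes, endpoints and analyses do not change.
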